Study Design	
Randomized, adaptive parallel arm study. Subjects will be initially screened during a screening period (+/- 7 days). During this screening period, subjects will sign an Informed Consent Form (ICF), have their weight/height and blood pressure measured as part of a physical exam, take a pregnancy test (females of child bearing potential), get blood drawn for analysis (blood lipids, HbA1c), and complete the PHQ-9 and pre-study survey. Subjects will be asked to complete their first batch of diaries to set a baseline hunger value.
 
At the end of the screening period, eligible subjects will be enrolled/randomized in the study and be randomized to either a treatment or control group. After enrolling, both control and treatment subjects will be instructed to follow a healthy diet and reduce calories as desired for the duration of the study and will receive training on the use of the electronic scale and completion of paper diaries. For the treatment group, subjects will be instructed on use of the Elira wearable patch system. Photographs will be taken at the enrollment visit. Following this, subjects will enter the Therapy Period for ~24-weeks.
 
At the 12 week visit, subjects will be assessed for weight loss, blood pressure, blood lipids, HbA1c, patient preference questionnaire and their participation will continue through months 4-6 for the Safety phase of the Therapy Period. The Therapy Period will be considered complete (pending laboratory results, adverse events or serious adverse events). Patient (treatment) photographs will also be taken at the 12 week visit.

Protocol #: CD-005; Version #: 4.0

Original Date: May 8, 2018 Revision Date: May 3, 2019

-Confidential-

	
The study utilizes an adaptive approach where cohorts of enrolled/randomized subjects (in groups of ~25 per arm) are assessed for dose response and progression to achievement of primary and secondary endpoints. Frequent interim endpoint assessment utilizing Markov-chain Monte Carlo (MCMC) methods coupled with Longitudinal analyses will be utilized to determine sample sizes for future cohorts (assessed primarily via Normal dynamic linear modeling [NDLM]). Long term safety of the device will be shown through 6 months of usage.

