
Statistical Analysis
	
Statistical Analysis Plan, 2019MAY31
 
ELIRA -2 Trial: Safety and Effectiveness of Transcutaneous Electrical Nerve Stimulation (TENS)-Assisted Weight Loss and/or Appetite Suppression
 
Protocol Number: CD-005, Original Date:2018MAY08, V4.1, Revised Date:2018AUG14
 
Signature Page
 
Author: [name] _____ Date _____
 
Approver: _____ Date _____
 
Approver: _____ Date _____
 
STATISTICAL CONSIDERATIONS AND ANALYSIS PLAN
 
General Methods
 
Categorical variables will be summarized by number and percent. Continuous variables will be summarized by total number (N), mean, standard deviation (SD), median, minimum and maximum. Ninety-five percent, 2-sided confidence intervals will be reported, as appropriate.
 
As this was a randomized trial, the groups are expected to be balanced on demographic and baseline characteristics. No formal testing for this is planned.
 
Planned analyses and summaries for the primary safety endpoint, co-primary efficacy endpoints, secondary efficacy endpoints and exploratory efficacy endpoints are detailed below.
 
Analysis Populations
 
The intent to treat (ITT) analysis population is defined as all subjects who were enrolled.
 
The modified intent to treat (mITT) analysis population is defined as all subjects who initiated therapy (i.e., initiated their first Treatment Period Visit) and had data through week 12. All safety and effectiveness analyses will be completed on the mITT analysis population.
 
The per protocol (PP) analysis population is defined as all subjects who met all inclusion/exclusion criteria, completed all visits in the study without any major protocol deviations. All effectiveness analyses will be completed on the PP analysis population.

------------------------------------	---

Safety Analyses

The primary safety endpoint is defined as the proportion of subjects free of TENS-related serious adverse events and adverse device effects through the therapy phase, safety success rate. The success rates will be compared between groups using chi-square test or Fisher's exact test, as appropriate.

Efficacy Analyses***Co-Primary Efficacy Analyses***

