5. STUDY DESIGN

[figure not shown]
Randomized, adaptive parallel arm study. Subjects will be initially screened during a screening period (1 week, ± 7 days; Figure 2). During this screening period, prior to study procedures being performed, subjects will sign an informed consent form. Then they will have their weight and blood pressure measured, FOCBP will have a pregnancy test, get blood drawn for analysis (blood lipids, HbA1c), and complete patient preference questionnaires. At the end of the screening/baseline period, eligible subjects will be offered the chance to enroll in the study. After enrolling, subjects will be randomized to treatment or control groups.

The Treatment group will be instructed to follow a healthy diet that they will follow for the duration of the study and will receive training on the use of the paper diaries, electronic scale, smartphone app and the Elira wearable patch system. All treatment subjects will be required to stimulate in the office for up to 30minutes to confirm sufficient system training and to acknowledge understanding stimulation settings. A below neck photograph will be taken of the treatment group in requested attire (i.e. biker shorts and sports bra for women, biker shorts for men). Following this, subjects will enter the Therapy Period, for a ~24-week duration. Treatment subjects may be contacted by PI or clinical coordinator to address any questions related to device functionality or compliance. Device usage will be monitored throughout therapy phase to ensure proper functionality and subject safety.

The Control group will be instructed to follow a healthy diet that they will follow for the duration of the study and will receive training on the use of the weekly paper diary and electronic scale. The Control group will not receive the electronic smartphone app or the Elira wearable patch system/components.

At the end of the 3 months of the Therapy Period, all subjects will be assessed for weight loss, blood pressure, blood lipids, HbA1c, and will continue to participate through months 4-6 to confirm the long term safety of the device prior to being terminated from the study. A below neck photograph will also be taken at the 12 week visit.

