7.3 SELECTION AND ENROLLMENT OF SUBJECTS

Prospective study subjects will be screened for study eligibility. A subject is considered enrolled after:

1. Written Informed Consent is obtained.
2. Meeting all inclusion and exclusion criteria and randomized into the study.
3. This study will utilize unique subject numbers for the purpose of trial data collection. Subjects signing an Informed Consent but not meeting all criteria will not be considered enrolled in the study, but the signed Informed Consents will be maintained by the PI for seven (7) years.

Following enrollment, subjects should remain in the study until completion of the required Therapy Phase.

A subject's participation may be discontinued for the following reasons:

- Subject Withdrawal: As subject participation in a clinical trial is voluntary, the subject may choose to discontinue participation at any time without penalty or loss of benefits.

- Investigator Termination: The Investigator may terminate the subject's participation without regard to the subject's consent if the Investigator believes termination is medically necessary.
- Lost-to-Follow-up: A subject is lost-to-follow up if he/she does not complete required follow-up, but has not "officially" withdrawn consent. In order to consider a subject lost to follow-up, site personnel should make all reasonable efforts to locate and communicate with the subject. A minimum of three (3) attempts to contact the subject should be recorded in the source documentation including date, time and name of site personnel attempting to make contact.

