8.1.2 Analysis Populations

The intent to treat (ITT) analysis population is defined as all subjects who were enrolled.

The modified intent to treat (mITT) analysis population is defined as all subjects who initiated therapy (i.e., initiated their first Treatment Period Visit) and had data through week 12. All safety and effectiveness analyses will be completed on the mITT analysis population.

The per protocol (PP) analysis population is defined as all subjects who met all inclusion/exclusion criteria, completed all visits in the study without any major protocol deviations. All effectiveness analyses will be completed on the PP analysis population.

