Safety analyses will be conducted an Intent to Treat (ITT) basis (i.e. all subjects who were enrolled). Primary and Secondary effectiveness analyses will be performed on a modified intent-to-treat basis (MITT; i.e. all subjects who initiated therapy, defined as subjects who initiated their first Treatment Period Visit) as will all per subject effectiveness analyses (e.g. responder analyses). Primary and Secondary endpoints (e.g. weight loss, appetite) will also be conducted on a completer, or per protocol basis (defined as those subjects that completed all visits in the study).

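### ITT rests on an enrolment definition that can be read to exclude randomised but ineligible subjects, and safety is assigned to two conflicting sets, neither of which reliably keeps every stimulated subject

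*Combined protocol and SAP*

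**What the plan says.** **ITT.** The Statistical Analysis part of the Protocol Summary and section 8.1.2 both state: "The intent to treat (ITT) analysis population is defined as all subjects who were enrolled".

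**Enrolment.** Three places describe it differently.
- Section 7.3 lists what must be true before a subject counts as enrolled. After written consent comes "Meeting all inclusion and exclusion criteria and randomized into the study". It adds: "Subjects signing an Informed Consent but not meeting all criteria will not be considered enrolled in the study".
- Section 5 puts enrolment first: "After enrolling, subjects will be randomized to treatment or control groups".
- The Study Design part of the Protocol Summary merges the two: "eligible subjects will be enrolled/randomized in the study and be randomized to either a treatment or control group".

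**Safety population.** Section 8.4 says: "Safety analyses will be conducted an Intent to Treat (ITT) basis (i.e. all subjects who were enrolled". Section 8.1.2 and the Protocol Summary say: "All safety and effectiveness analyses will be completed on the mITT analysis population". On the latter set: "The modified intent to treat (mITT) analysis population is defined as all subjects who initiated therapy", with the further condition of having data through week 12. Section 8.4 describes mITT without that condition.

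**Safety endpoint.** Section 8.1.3 compares between groups the proportion of subjects free of TENS-related serious adverse events and adverse device effects through the therapy phase.

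**The concern.** An ITT set should be fixed by the act of randomisation. Here it is fixed by a term whose only formal definition also contains eligibility. That allows a reading in which a subject is removed after randomisation because of something learned later, in an open-label trial where the outcome may already be known.

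Safety is where this could matter. Some criteria concern the device itself: exclusion 7.2.17 covers inability to tolerate stimulation as well as allergy to electrode materials, 7.2.18 covers a history of sensitive skin, and inclusion 7.1.4 requires the ability to wear and use the patch. Tolerance of stimulation is first tested after randomisation, at Visit 1, in Treatment subjects only. A skin reaction could thus lead to a finding that the subject never met a criterion, and such subjects are the ones the safety endpoint is meant to count.

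The alternative set, mITT, has its own gap. The Visit Schedule in the Protocol Summary allows that severe irritation may end a subject's participation. If that happens before week 12, the subject has no data through week 12 and is not in mITT.

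**Working it through.** The plan gives no figure for this point, so the check is mainly a comparison of definitions.

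**Step 1. Who is in each set, read literally?**

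| Subject | ITT via section 7.3 | ITT via section 5 | mITT in 8.1.2 |
|---|---|---|---|
| Randomised, eligible, data through week 12 | in | in | in, if therapy begun |
| Randomised and stimulated, later found never to have met a criterion, data through week 12 | can be read as out | in | in |
| Randomised and stimulated, eligible, leaves before week 12 | in | in | out |
| Randomised and stimulated, later found ineligible, leaves before week 12 | can be read as out | in | out |
| Enrols but leaves before allocation | out | in, with no arm | out |

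The second row shows that mITT need not be a subset of ITT. The fourth row is the subject whom neither the section 7.3 reading of ITT nor mITT keeps. A subject who was eligible at randomisation and later stops meeting a criterion stays enrolled on every reading.

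**Step 2. How many subjects could the ITT wording touch?** No rate is given. Assuming 1% to 5% late ineligibility:
- of the 160 subjects in section 8.2: 160 × 0.01 = 1.6 to 160 × 0.05 = 8;
- of the 300 maximum in the Protocol Summary: 300 × 0.01 = 3 to 300 × 0.05 = 15.

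**Step 3. What could that do to the safety success rate?** Take 80 Treatment subjects (section 8.2). Assume *e* subjects with a device event who stay in the set, and *k* further subjects with a device event who are excluded.
- All randomised: (80 − e − k)/80
- Excluding the k: (80 − e − k)/(80 − k)

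With e = 4:

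| k | All randomised | Excluding k | Difference (points) |
|---|---|---|---|
| 1 | 75/80 = 93.75% | 75/79 = 94.94% | 1.19 |
| 2 | 74/80 = 92.50% | 74/78 = 94.87% | 2.37 |
| 3 | 73/80 = 91.25% | 73/77 = 94.81% | 3.56 |
| 4 | 72/80 = 90.00% | 72/76 = 94.74% | 4.74 |

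The choice of e matters little. With e = 0 the difference runs from 1.25 (98.75% to 100%) to 5.00 (95.00% to 100%). With e = 8 it runs from 1.12 (88.75% to 89.87%) to 4.47 (85.00% to 89.47%).

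**Step 4. How many could the week-12 condition touch?** Section 8.2 assumes 30% dropout without saying when it occurs. That is 80 × 0.30 = 24 per group, so up to 24 of 80 could be missing from mITT if all of it fell before week 12. The effect on the safety rate depends on how many of them had device events, which the documents do not say.

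**The case against.** The strongest reply is that section 7.3 is a screen-failure rule. It opens with screening, and its sentence on subjects who do not meet criteria ends with how long their consent forms are kept. It then says enrolled subjects should remain in the study, and its reasons for discontinuation do not include a late finding of ineligibility. Other text points the same way:
- Section 13.3 treats an eligibility violation as a major deviation and says nothing of cancelling enrolment.
- The per-protocol set applies eligibility as its own filter, which would be redundant if ITT were already restricted.
- Section 6.1.1 tabulates safety for all subjects, including those discontinued, and section 8.3 says partial data from dropouts will be included.

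This is good evidence of intent. A reader might infer that an ineligible randomised subject definitely drops out of ITT; the documents do not support that. But none of these places says that ITT is all randomised subjects, and the deviation and tabulation rules do not assign anyone to an analysis set.

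Three further inferences also go too far. First, that no reading of ITT covers everyone randomised: under section 5 all of them are included. Second, that only Treatment subjects have eligibility looked at again: section 9 and Appendix 6 recheck criteria in both arms at every visit. What remains is narrower. The repeat dermatome assessments after Visit 1 and the tolerance check are for Treatment subjects only. Third, that the trial's success decision is exposed: the co-primary ANCOVA is on mITT, whose definition does not refer to enrolment.

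**Conclusion.** The point holds as an ambiguity in ITT together with an outright contradiction over the safety population. ITT can be read to exclude randomised subjects later found ineligible. Safety is on ITT in section 8.4 and on mITT in section 8.1.2 and the Protocol Summary. Either choice, as written, can lose stimulated subjects: ITT through eligibility, mITT through the week-12 condition. The second route may well be the larger, given the 30% dropout assumed.

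The size is unknown. For the ITT wording it is nil if enrolled means randomised or if no such subject arises. It is about 1 to 5 percentage points on the Treatment safety success rate if 1 to 4 of 80 Treatment subjects with device events were excluded. Those counts, and the number of other events, are assumptions. The illustration is also one-sided, because it removes only subjects with events. The ITT wording does not affect the efficacy success test. The change should be made, because the text is easily repaired and the set that carries safety should not depend on which section is followed.

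**What to change.** 1. In section 8.1.2 and the Protocol Summary, define ITT as all randomised subjects, analysed in the arm assigned, whatever is later learned about eligibility.
2. Define one safety set as all randomised subjects, with anyone who received stimulation counted under Treatment. Use it in 8.1.2, 8.1.3, 8.4 and the Protocol Summary in place of the conflicting ITT and mITT statements.
3. Use eligibility failures only to define the per-protocol set.
4. Align section 5, section 7.3 and the Protocol Summary so that enrolled means randomised, and limit the not-enrolled sentence in 7.3 to subjects who fail screening before randomisation.

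The cost is protocol and SAP wording only; no extra data or subjects are needed. The downside is that a few ineligible subjects stay in ITT and may slightly dilute effects; the per-protocol analysis already planned shows the results without them.

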To further understand the time points and weekly diary entries on appetite suppression, all time points and weekly entries will be analyzed in a repeated measures analysis of variance (RMANOVA) for each of the four appetite suppression endpoints separately. The RMANOVA will not use percentage changes but will use the actual appetite suppression scores with a factor for group treatment, time (week and time point), as well as the interaction factor between time and treatment.

The occurrence rate for subjects experiencing >5% TBWL at the end of 3 months will be compared between groups using chi-square test or Fisher's exact test, as appropriate.

Blood pressure, blood lipids, and HbA1c at the end of 3 months of the Therapy compared to Baseline between groups using t-tests or Wilcoxon rank sum tests, as appropriate.

The percent change from baseline in BMI at the end of 3 months of the Therapy compared to Baseline between groups using t-tests or Wilcoxon rank sum tests, as appropriate.

Exploratory Efficacy Summaries

Summary statistics will be provided by visit and by group for the other time points (besides the 3 month time point) for percent change from baseline in appetite suppression scores, %TBWL, occurrence rate for >5% TBWL, blood pressure, blood lipids, and HBA1c. In addition, summary statistics will be provided by visit and by group for ease of use, prevalence of use errors associated with patch unit and dietary application, and preference scores.

Justification of Sample Size

As per the protocol, the calculation sample size for the study is based on conservative imputation of results from other studies on weight loss including the use of TENS for weight loss. The degree of coaching/dietary support throughout the present study is moderate intensity lifestyle/weight coaching. The sample size modeling assumes an average of 3.5% TBWL in Control Subjects using diet and exercise alone. The estimated weight loss in Treatment Subjects is modeled from preliminary data on T6/T7 dermatomal TENS when used for weight loss: 6% TBWL. The variance of the responses in the study (i.e. Standard Deviation) was modeled at +/- 5% TBWL. This value was taken from previous dermatomal TENS weight loss study results. The model assumes a 30% drop out rate across groups and an 80% powered endpoint using an adaptive p spending model wherein interim posterior probability assessments are allowed after enrolling proscribe cohorts of not less than 67% of subjects. The alpha penalty will be minimized per interim by assessing the relationship between stimulation (i.e. dose) and weight loss using Normalized Linear Dynamic Modeling (NLDM) to determine overall sample size projected (i.e. futility) rather than assessing the primary hypothesis per se. Monotonicity will not be assumed in this analysis. This modeling provides an estimate of 80 subjects per group, for a total study size of 160 subjects. However, the protocol allows for enrollment of additional subjects should the interim model project under powering of the primary endpoint.

Handling of Missing Data

Every effort will be made to collect all data at each time point in the study. The PI and the Clinical Data Monitor will minimize the amount of missing data by appropriate management of

Protocol #: CD-005; **Version #:** 4.0

Original Date: May 8, 2018 **Revision Date:** May 3, 2019

-Confidential-

	
the prospective clinical trial, proper screening of subjects, and training of clinicians. If a subject misses a dietary entry in to either the paper or electronic diary, a look back entry for that value is allowed provide for the week preceding the event. Outside this window, data will be considered missing. All partial data available for subjects who drop out during the course of the study will be included.
 
Missing data will only be imputed for the co-primary endpoints. The LOCF method will be utilized at the 3 month time point for the two co-primary endpoints of percent change from baseline in appetite suppression scores and %TBWL. The ANCOVA analysis with LOCF on the mITT population for the co-primary endpoints were planned for the main analyses for the study to determine study success. Note, however, by definition, the mITT population may not need LOCF as only those with a week 12 visit will be included in the mITT population. A patient, however, may have had a week 12 visit but have missing data on some or all co-primary endpoints, in which case LOCF methods will be used.
 
To assess the potential effect of missing data on the co-primary effectiveness endpoints, a tipping point analysis will be computed for each co-primary endpoint on the mITT population. If none of the 5 co-primary endpoints are missing at week 12, the tipping point analysis will be a moot point and will not be conducted. A tipping point analysis involves imputing each missing data point, one-at-a-time until the study conclusion is tipped in the other direction (i.e., from statistically significant to non-statistically significant or vice versa, from non-statistically significant to statistically significant).

Risk/Benefit Analysis
	
If shown to be safe and effective, the therapy could eventually provide overweight/ moderately obese subjects a low risk option for appetite suppression and weight loss beyond diet and lifestyle modification alone.
 
The potential adverse events and adverse device effects and risks associated with this study and the use of the patch System are identical to those normally associated with standard TENS system used for pain control and similar indications.

CONTACT LIST

Study Sponsor	ELIRA, Inc.
Coordinating Principal Investigators	[name] and [name]
Study Monitor	[name]
Data Management	[name] BSN
Statistical Analysis	[name]
Data Safety Monitoring Board	[name]

